3.8.4. Multiple Comparison/Multiplicity

The study will be claimed positive when the primary analysis of the primary efficacy endpoint is statistically significant. The primary endpoint will be tested at a full α level of 0.05. To control the overall Type I error rate of the primary and secondary endpoints, hierarchical testing will be performed in the following order: (1) percent change from baseline in body weight at Week 12, (2) proportion of subjects with $\geq 10\%$ weight gain from baseline at Week 12, (3) proportion of subjects with $\geq 7\%$ weight gain from baseline at Week 12, (4) change from baseline in waist circumference at Week 12, (5) change from baseline in CGI-S score within the ALKS 3831 Group at Week 12.

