### 7.1. Subject Inclusion Criteria

Each subject must meet all of the following inclusion criteria to qualify for participation in this study.

1. Subject is willing and able to give informed consent/assent, as per local requirements
2. Subject meets the following antipsychotic treatment and duration of illness eligibility requirements:
  - Subject has less than 24 weeks previous treatment with antipsychotics (cumulative; lifetime)
    - Subject treated with aripiprazole can receive an additional 1 year of treatment at  $\leq 5$  mg/day, and this treatment will not be considered as part of the 24 weeks of previous treatment with antipsychotics
  - Subject has less than 4 years elapse since the initial onset of active phase of symptoms
  - For subjects currently taking antipsychotic medication, the subject and the treating physician feel that a switch in medication is needed (ie, unsatisfactory clinical response, AEs, or nonadherence to current medication)
3. For US sites, subject is  $\geq 16$  and  $< 40$  years of age at Screening. For subjects  $\geq 16$  and  $< 18$  years of age, must have had previous antipsychotic exposure. For non-US sites, subject is  $\geq 18$  and  $< 40$  years of age at Screening
4. Subject has a BMI  $< 30.0$  kg/m^2 at Screening
5. Subject agrees to use an acceptable method of contraception for the duration of the study and for 30 days after any study drug administration, unless surgically sterile or postmenopausal (please refer to [Section 8.4.1](#) for additional details regarding contraception)
6. Subject meets the Diagnostic and Statistical Manual of Mental Disorders-Fifth Edition (DSM-5) criteria for a primary diagnosis of schizophrenia, schizopreniform disorder, or bipolar I disorder, confirmed with the Mini International Neuropsychiatric Interview 7.0 for Schizophrenia and Psychotic Disorder Studies (MINI v7.0) for subjects  $\geq 18$  years of age, or with the Mini International Neuropsychiatric Interview for Children and Adolescents 7.0 for Schizophrenia and Psychotic Disorder Studies (MINI KID v7.0) for subjects 16 to  $< 18$  years of age at Visit 1
7. For subjects with bipolar I disorder, they must have been experiencing an episode of acute mania as defined by DSM-5 within the last 14 days prior to Visit 1

8. Subject is suitable for eventual outpatient treatment based on the opinion of the Investigator and review of medical and clinical history by the Sponsor (or designee)

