2. SAMPLE SIZE CONSIDERATION

Approximately 425 subjects will be enrolled in order to have 400 subjects (200 per treatment group) in the primary efficacy population, which is defined in Section 3.2.2. Assuming the percent weight gain at Week 12 is 5% and 8.5% for ALKS 3831 and olanzapine groups, respectively, a common standard deviation of 8%, and a cumulative dropout rate of 35%, 200 subjects per treatment group (400 subjects in total) will provide at least 90% power to demonstrate a difference of ALKS 3831 relative to olanzapine at a two-sided significance level of 0.05.

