3. DATA ANALYSIS

3.1. General Statistical Methodology

Baseline for the efficacy or safety analysis is defined as the last non-missing efficacy or safety assessment on or before the first dose of double-blind study drug.

In general, descriptive statistics: n, mean, standard deviation (SD), median, minimum, and maximum, for continuous variables and number and percentage of subjects in each category for categorical variables will be provided by treatment group for all endpoints.

The metabolic laboratory parameters will be analyzed on a linear and log-transformed scale. If log-transformed data is not normally distributed, Wilcoxon rank sum test and Hodges-Lehmann estimator will be used.

All statistical tests and confidence intervals (CIs), unless stated otherwise, will be 2-sided and will be set at an alpha level of 0.05.

All source data will be presented as subject data listings.

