To assess the change from baseline in CGI-S at Week 12 within the ALKS 3831 Group, the MMRM will be used. The model will include treatment, visit, treatment-by-visit interaction and all randomization strata as factors. An unstructured variance-covariance matrix will be used. The least squares (LS) mean, 95% CI and p-value of change from baseline at Week 12 within the ALKS 3831 Group will be reported.

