3.8.6. Other Endpoints

Other endpoints include:

- Absolute change from baseline in body weight by visit
- Absolute change from baseline in BMI by visit
- Proportion of subjects in each BMI category (normal weight: <25 , overweight: ≥ 25 to <30 , obese: $\geq 30 \text{ kg/m}^2$) by visit and proportion of subjects with shifts in BMI category from baseline by visit

- Proportion of subjects with ≥ 5 cm increase from baseline in waist circumference at Week 12
- Body composition endpoints, as assessed by bioimpedance analysis, including:
 - Change from baseline in fat mass by visit
 - Change from baseline in percent body fat by visit
 - Change from baseline in fat mass index by visit
 - Change from baseline in visceral adipose tissue by visit
 - Change from baseline in lean mass by visit
 - Change from baseline in fat free mass index by visit
 - Change from baseline in total skeletal muscle mass by visit
- Percent and absolute change from baseline in fasting lipids (fasting triglycerides, low-density lipoprotein [LDL], high-density lipoprotein [HDL], total cholesterol), fasting glucose, hemoglobin A1c (HbA1c), fasting insulin, and homeostatic model assessment of insulin resistance (HOMA-IR) by visit
- Percent and absolute change from baseline in additional laboratory parameters including apolipoprotein B (Apo B), apolipoprotein A1 (Apo A1), Apo B/Apo A1, high-sensitivity C-reactive protein (hs-CRP), interleukin-6 (IL-6) and tumor necrosis factor α (TNFa) by visit
- Change from baseline in blood pressure (supine systolic and diastolic) by visit
- Proportion of subjects in each blood pressure category (normal, elevated, stage 1 hypertension, stage 2 hypertension) and proportion of subjects shifting from normal or elevated blood pressure at baseline to Stage 1 or 2 hypertension by visit
- Proportion of subjects meeting criteria for metabolic syndrome by visit and proportion of subjects shifting from no metabolic syndrome at baseline to having metabolic syndrome by visit
- Proportion of subjects meeting individual metabolic syndrome component criterion by visit
- Change from baseline in CGI-S score (between and within treatment groups) by visit
- Change from baseline in CGI-S score (between and within treatment groups) by visit and by diagnosis
- CGI-I score by visit
- Change from baseline in IWQOL-Lite score by visit

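### The last test in the error-controlled hierarchy is a one-arm before-after change in CGI-S, which carries no comparative or causal evidence and belongs among the descriptive results

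*SAP*

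**What the plan says.** SAP 3.8.4 states the purpose of the sequence: "To control the overall Type I error rate of the primary and secondary endpoints, hierarchical testing will be performed in the following order". Items 1 to 4 are randomized comparisons: percent weight change, the two weight-gain proportions and waist circumference. Item 5 is "5) change from baseline in CGI-S score within the ALKS 3831 Group at Week 12". Protocol 14.4 and the synopsis give the same order, and Protocol 11.2 lists item 5 among the secondary efficacy endpoints.

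SAP 3.8.3.4 gives the method: "To assess the change from baseline in CGI-S at Week 12 within the ALKS 3831 Group, the MMRM will be used". The model contains both arms, but the reported result does not: "The least squares (LS) mean, 95% CI and p-value of change from baseline at Week 12 within the ALKS 3831 Group will be reported". No null hypothesis is written for this test, no contrast with olanzapine is part of it, and neither document gives a non-inferiority margin for CGI-S.

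The randomized comparison appears in SAP 3.8.6, among the other endpoints: "Change from baseline in CGI-S score (between and within treatment groups) by visit". For all endpoints in that group, SAP 3.8.6 limits presentation to the estimated effect, its 95% CI and/or descriptive statistics.

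Protocol 5.3 says that every subject receives active antipsychotic treatment and that efficacy is expected to be similar in the two arms.

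**The concern.** Type I error control at step 5 protects the null as implied, namely that mean CGI-S does not change over 12 weeks in subjects given ALKS 3831. A reader of a confirmed secondary efficacy endpoint will usually have a different question in mind: whether the drug caused the improvement, or whether adding samidorphan left olanzapine's efficacy intact. A one-arm change answers neither.

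The protocol leaves several routes to improvement open other than an effect of ALKS 3831:

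- For bipolar I subjects, Protocol 7.1 says that "they must have been experiencing an episode of acute mania as defined by DSM-5 within the last 14 days prior to Visit 1".
- Subjects already on an antipsychotic enter because a switch is thought necessary, and unsatisfactory response is one of the listed reasons (Protocol 7.1).
- Supportive clinical care, which may include individual psychotherapy, is offered during treatment (Protocol 8.3.10).
- An SSRI may be started during treatment (Protocol 8.4.3).

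Even a genuine drug effect could be olanzapine's alone. At stake is a formally error-controlled statement that the design cannot attribute to the product, while the randomized contrast that bears on similar efficacy has no place in the hierarchy.

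**Working it through.** **The plan's own figure.** The only power statement concerns the primary endpoint. SAP section 2 reads "Assuming the percent weight gain at Week 12 is 5% and 8.5% for ALKS 3831 and olanzapine groups, respectively", with SD 8%, 35% dropout, 200 per arm and at least 90% power. Completers per arm are 200 × 0.65 = 130. Power is Φ(Δ/(SD·√(2/n)) − 1.96).

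- n = 130: 3.5/(8 × √(2/130)) = 3.53, so power is Φ(1.57) = 94.1%.
- n = 200: 3.5/(8 × √(2/200)) = 4.375, so power is Φ(2.415) = 99.2%.

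The stated figure holds. No power or SD is stated for CGI-S.

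**Inputs for step 5.**

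- Alpha: tests "will be 2-sided and will be set at an alpha level of 0.05" (SAP 3.1).
- Sample size: 130 (completers) to 200 (all FAS subjects in the arm), from SAP section 2.
- SD of CGI-S change: not in the documents; assumed 0.8 to 1.5.
- Background change d, meaning change not due to drug: not in the documents; varied from 0 to 0.5 points.

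**Formula.** With SE = SD/√n, the smallest significant mean change is 1.96·SE. The chance of significance is Φ(d/SE − 1.96) + Φ(−d/SE − 1.96). This one-sample calculation approximates the planned MMRM, which also uses earlier visits; the two sample sizes are meant to bracket its effective information.

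**Example, SD 1.0 and n = 130.** SE = 1/√130 = 0.0877, so a mean change of 1.96 × 0.0877 = 0.17 points is significant. At d = 0.3, d/SE = 3.42 and Φ(3.42 − 1.96) = 92.8%. With n = 200 the threshold is 0.14 points.

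**Chance of significance from background change alone:**

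| d (points) | n=130, SD 0.8 | n=130, SD 1.0 | n=130, SD 1.5 | n=200, SD 0.8 | n=200, SD 1.0 | n=200, SD 1.5 |
|---|---|---|---|---|---|---|
| 0 | 5% | 5% | 5% | 5% | 5% | 5% |
| 0.1 | 29.7% | 20.7% | 11.8% | 42.4% | 29.3% | 15.6% |
| 0.2 | 81.3% | 62.6% | 33.0% | 94.2% | 80.7% | 47.0% |
| 0.3 | 99.0% | 92.8% | 62.6% | >99% | 98.9% | 80.7% |
| 0.5 | about 100% | about 100% | 96.7% | about 100% | about 100% | 99.7% |

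The background change that gives a 90% chance of significance is (1.96 + 1.28)·SE. It runs from 0.18 points (n = 200, SD 0.8) to 0.43 points (n = 130, SD 1.5).

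**Contrast with the randomized comparison.** In 20,000 simulated trials with SD 1.0 and the same 0.3-point improvement in both arms, the within-arm t-test was significant in 92.4% (n = 130) and 98.8% (n = 200). The between-arm t-test on the same data was significant in 4.7% and 5.2%.

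**Precision of the between-arm estimate.** The 95% CI half-width is 1.96·SD·√(2/n). At SD 1.0 this is 0.24 points (130 per arm) or 0.20 (200 per arm). Over SD 0.8 to 1.5 it runs from 0.16 to 0.37.

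**The case against.** The case for leaving item 5 alone has real content.

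- Background improvement is not certain. Inclusion requires no minimum CGI-S, so regression to the mean through selection on that score is not built in. CGI-S is first rated at Visit 2, and screening may last 30 days, so some recovery from mania may precede baseline. Switch reasons include adverse events and nonadherence. Earlier antipsychotics and mood stabilizers are tapered off by Week 2, which could worsen scores. Supportive care is optional.
- The endpoint is labelled as within-group throughout, and neither document says that it will support a claim of antipsychotic efficacy. The stated objectives are weight, then safety and tolerability.
- The test comes last, is reached only if four others succeed, and has no bearing on whether the study is positive.
- The between-arm CGI-S analysis is already planned.

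The first point stands against a stronger reading. A reader might infer that the test would be significant whatever the drug does. The documents give no SD or natural course to support that, and with no background change the rejection rate is the nominal 5%. A reader might also infer that the result has no evidential value. That goes too far as well, because the estimate and CI show whether subjects on ALKS 3831 improved or worsened. Nor do the documents support a reading that familywise error is inflated or that the weight results are compromised.

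What the objections do not answer is attribution. An honest label does not turn a before-after change into a drug effect, and inclusion in the hierarchy gives it the same formal standing as four randomized comparisons.

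**Conclusion.** The point holds as one of attribution and status. Step 5 is a confirmatory test of an uncontrolled within-arm change, in a trial without placebo and with olanzapine in both arms. It could well be significant from background change or from olanzapine alone, so it offers no comparative or causal evidence about ALKS 3831.

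How readily it would be significant depends on quantities that the documents do not give. Over the assumed range, background changes of about 0.2 to 0.4 points are enough for a 90% chance of significance, and at 0.1 points the chance is 12 to 42%. The reach is limited to this single secondary claim.

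**What to change.** Remove item 5 from the hierarchy in the Protocol synopsis, Protocol 14.4 and SAP 3.8.4. Keep the within-arm Week 12 change with its 95% CI as a descriptive result.

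State that any conclusion about antipsychotic efficacy rests on the between-arm LS-mean difference with its 95% CI. Since SAP 3.8.6 allows an estimate with CI and/or descriptive statistics, commit explicitly to the estimate and CI for this endpoint. If the sponsor wants a confirmatory claim of preserved efficacy, that needs a between-arm margin, specified in advance and justified; the half-widths above indicate the precision available under the assumed SDs.

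In the same revision, reconcile the CGI-S model. Protocol 14.4 includes baseline CGI-S as a covariate, but SAP 3.8.3.4 does not list it, and the between-arm analysis refers back to that section.

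The cost is one nominal secondary claim and an amendment. SAP section 5 calls for a protocol amendment when key secondary hypotheses change before unblinding, and Protocol 17.1 requires ethics re-approval of amendments. No new data are needed.

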3.8.5. Examination of Subgroups

Subgroup analyses of the primary and secondary endpoints will be performed for each of the following categories:

- Diagnosis (schizophrenia/schizopreniform disorder, bipolar I disorder)
- Sex (male, female)
- Age (<18 years, ≥ 18 years)
- Age (<30 years, ≥ 30 years)
- Race (Black or African American, Non-Black or Non-African American)
- Baseline BMI ($<25 \text{ kg/m}^2$, $\geq 25 \text{ kg/m}^2$)
- Region (US, Non-US)

A forest plot of the estimated treatment effect along with 95% CIs will be provided by the subgroup factors listed above. Only summary statistics for the age <18 years subgroup will be provided due to its limited enrolment expected.

3.8.6. Other Endpoints

Other endpoints include:

- Absolute change from baseline in body weight by visit
- Absolute change from baseline in BMI by visit
- Proportion of subjects in each BMI category (normal weight: <25 , overweight: ≥ 25 to <30 , obese: $\geq 30 \text{ kg/m}^2$) by visit and proportion of subjects with shifts in BMI category from baseline by visit

- Proportion of subjects with ≥ 5 cm increase from baseline in waist circumference at Week 12
- Body composition endpoints, as assessed by bioimpedance analysis, including:
 - Change from baseline in fat mass by visit
 - Change from baseline in percent body fat by visit
 - Change from baseline in fat mass index by visit
 - Change from baseline in visceral adipose tissue by visit
 - Change from baseline in lean mass by visit
 - Change from baseline in fat free mass index by visit
 - Change from baseline in total skeletal muscle mass by visit
- Percent and absolute change from baseline in fasting lipids (fasting triglycerides, low-density lipoprotein [LDL], high-density lipoprotein [HDL], total cholesterol), fasting glucose, hemoglobin A1c (HbA1c), fasting insulin, and homeostatic model assessment of insulin resistance (HOMA-IR) by visit
- Percent and absolute change from baseline in additional laboratory parameters including apolipoprotein B (Apo B), apolipoprotein A1 (Apo A1), Apo B/Apo A1, high-sensitivity C-reactive protein (hs-CRP), interleukin-6 (IL-6) and tumor necrosis factor α (TNFa) by visit
- Change from baseline in blood pressure (supine systolic and diastolic) by visit
- Proportion of subjects in each blood pressure category (normal, elevated, stage 1 hypertension, stage 2 hypertension) and proportion of subjects shifting from normal or elevated blood pressure at baseline to Stage 1 or 2 hypertension by visit
- Proportion of subjects meeting criteria for metabolic syndrome by visit and proportion of subjects shifting from no metabolic syndrome at baseline to having metabolic syndrome by visit
- Proportion of subjects meeting individual metabolic syndrome component criterion by visit
- Change from baseline in CGI-S score (between and within treatment groups) by visit
- Change from baseline in CGI-S score (between and within treatment groups) by visit and by diagnosis
- CGI-I score by visit
- Change from baseline in IWQOL-Lite score by visit

For all the other endpoints, presentation of analysis results will be limited to estimated treatment effect, 95% CI and/or descriptive statistics.

Absolute change in body weight, BMI, systolic and diastolic blood pressure and all body composition endpoints will be analyzed similarly by ANCOVA model and MI for missing data

as noted in [Section 3.8.2.1](#). The ANCOVA model will include treatment and all randomization strata as factors and baseline value as a covariate. The proportion of subjects with ≥ 5 cm increase of waist circumference will be analyzed by the logistic regression model and MI method in a similar fashion as the proportion of subjects with $\geq 10\%$ weight gain, using the same imputed dataset from the primary analysis of change from baseline in waist circumference in [Section 3.8.3.3](#).

The proportion of subjects in each BMI category will be analyzed based on each subject's by-visit assessment status using a logistic regression model including treatment group and randomization strata as factors, and baseline BMI as covariate. The model is based on the MI for missing postbaseline assessments. Rubin's rule is used to combine results from applying the logistic regression model on imputed datasets.

Proportion of subjects with shifts in BMI category by visit will also be analyzed based on each subject's by-visit assessment status using the logistic regression model mentioned above. Shifts are defined as follows:

- Proportion of subjects shifting from $\text{BMI} < 25 \text{ kg/m}^2$ at baseline to $\text{BMI} \geq 25 \text{ kg/m}^2$ by visit
- Proportion of subjects shifting from $\text{BMI} < 30 \text{ kg/m}^2$ at baseline to $\text{BMI} \geq 30 \text{ kg/m}^2$ by visit

The proportion of subjects in each blood pressure category will be analyzed based on the subject's by-visit assessment status using a logistic regression model including treatment group and randomization strata as factors, and baseline systolic and diastolic blood pressure as covariates. The model is based on the MI for missing postbaseline assessments. Rubin's rule is used to combine results from applying the logistic regression model on imputed datasets.

Number of responders and proportion for each blood pressure category are the mean number of responders and mean proportion from the imputed datasets, respectively.

Proportion of subjects with shifts in blood pressure category by visit will also be analyzed based on each subject's by-visit assessment status using the logistic regression model described above. Shifts are defined as follows:

- Proportion of subjects shifting from Normal blood pressure at baseline to Stage 1 or Stage 2 Hypertension
- Proportion of subjects shifting from Normal or Elevated blood pressure at baseline to Stage 1 or Stage 2 Hypertension

The blood pressure categories will be defined as follows based on American Heart Association criteria:

- Normal: systolic and diastolic blood pressure of < 120 and $< 80 \text{ mmHg}$, respectively
- Elevated: systolic and diastolic blood pressure of ≥ 120 to ≤ 129 and $< 80 \text{ mmHg}$, respectively
- Stage 1: systolic blood pressure of ≥ 130 to $\leq 139 \text{ mmHg}$ or diastolic blood pressure of ≥ 80 to $\leq 89 \text{ mmHg}$

- Stage 2: systolic blood pressure of ≥ 140 mmHg or diastolic blood pressure of ≥ 90 mmHg.

The following laboratory parameters will be analyzed by MMRM model as described in [Section 3.8.3.4](#). The model will include treatment, visit, treatment-by-visit interaction, all randomization strata as categorical fixed effects; the baseline value will be included as the covariate. An unstructured variance-covariance matrix will be used.

- Percent and absolute change from baseline in fasting lipids (fasting triglycerides, LDL, HDL, total cholesterol), fasting glucose, HbA1c, fasting insulin, and HOMA-IR by visit
- Percent and absolute change from baseline in additional laboratory parameters including Apo B, Apo A1, Apo B/Apo A1, hs-CRP, IL-6 and TNFa by visit.

The proportion of subjects with metabolic syndrome at each visit will be analyzed by logistic regression model including treatment group and randomization strata as factors and baseline metabolic syndrome as covariate.

The proportion of subjects meeting each individual component criterion for metabolic syndrome (listed below) will be analyzed by visit using the same logistic regression model described above with the respective baseline value for each component as the covariate.

Additionally, a similar logistic regression model including treatment and randomization strata as factors will be used to analyze the proportion of subjects shifting from no metabolic syndrome at baseline to developing metabolic syndrome postbaseline. Data are based on observed values with no imputation for missing values.

Metabolic syndrome is defined as meeting at least 3 of the following individual component criteria:

- Waist circumference, cm > 88 (women), > 102 (men)
- Triglycerides, mg/dL ≥ 150
- HDL cholesterol, mg/dL < 50 (women), < 40 (men)
- Glucose, fasting mg/dL ≥ 100
- Blood pressure, mm Hg $\geq 130/85$

The following endpoints will be analyzed by MMRM model as described in [Section 3.8.3.4](#), as applicable.

- Change from baseline in CGI-S score (between and within treatment groups) by visit
- Change from baseline in CGI-S score (between and within treatment groups) by visit and by diagnosis
- Change from baseline in IWQOL-Lite score by visit

IWQOL-Lite scale is a 31-item self-report measure of obesity-specific quality of life. The IWQOL-Lite provides an overall total score as well as scores on five domains: (1) physical function, (2) self-esteem, (3) sexual life, (4) public distress, and (5) work. The raw IWQOL scores will be transformed as follows ([Tessier et al, 2012](#)) before analyzed by the MMRM

method. The transformed scores range from 0 to 100, with 100 representing the best and 0 the most impaired quality of life.

$$\text{Transformed Score} = \frac{\text{maximum theoretical score} - \text{actual score}}{\text{test score range}} \times 100$$

CGI-I score and CGI-I responder status (≤ 2 versus > 2) at each visit will be summarized by treatment group. Descriptive statistics will be presented.

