1.2 Summary of the Study Design

This is a Phase 3, multicenter, randomized, double-blind study to evaluate the effect of ALKS 3831 compared to olanzapine on body weight in young adults with schizophrenia, schizophreniform disorder, or bipolar I disorder who are early in their illness.

Subjects will be screened at Visit 1, up to 30 days prior to randomization. At Visit 2, eligible subjects will be randomized 1:1 to ALKS 3831 or olanzapine, and receive study drug for up to 12 weeks. Randomization will be stratified by diagnosis (schizophrenia/schizophreniform disorder vs bipolar I disorder), region (US vs non-US), and baseline BMI (<25 vs ≥ 25). Subjects on antipsychotic medications or mood stabilizers (excluding study medication) should be tapered off this medication by the end of week 2 (Visit 4). Subjects may be inpatient or outpatient at Screening; however, in the opinion of the Investigator, all subjects should be appropriate for eventual outpatient treatment. Subjects should be outpatient within 2 weeks post randomization. Cases that require inpatient treatment for longer than 2 weeks will require review and approval by the Medical Monitor on a case by case basis.

Starting with Week 2 (Visit 4), subjects will come for bi-weekly visits for the remaining 10 weeks. Study drug will be provided to subjects as coated bilayer tablets dispensed in blister packs at each visit to be taken at home (one tablet by mouth each day, preferably at bedtime). For the first week, at the discretion of the Investigator, subjects will receive 5, 10, 15 or 20 mg of olanzapine, or 5/10¹, 10/10, 15/10 or 20/10 mg of ALKS 3831. At the end of Week 1, for subjects initiated on 5 mg of olanzapine or 5/10 mg of ALKS 3831, the dose will be increased to 10 mg of olanzapine or 10/10 mg of ALKS 3831. For all other subjects, the dose may also be increased to either 15 or 20 mg of olanzapine, or 15/10 or 20/10 mg of ALKS 3831. Following this increase, the dose may be increased or decreased to 5, 10, 15, or 20 mg of olanzapine, or to 5/10, 10/10, 15/10, or 20/10 mg of ALKS 3831 at the Investigator's discretion. Dosing will be

¹ ALKS 3831 dose is represented as XX/XX where the first number represents the OLZ dose in mg and the second number represents the SAM dose in mg.

[figure not shown]

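### The waist and HDL component models for metabolic syndrome adjust for baseline value without sex although both cut-offs are sex-specific: a minor, avoidable loss of efficiency

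*SAP*

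**What the plan says.** Metabolic syndrome appears only in the SAP, under 3.8.6 Other Endpoints. The syndrome itself is analysed by logistic regression "including treatment group and randomization strata as factors and baseline metabolic syndrome as covariate". Each component criterion is then analysed "using the same logistic regression model described above with the respective baseline value for each component as the covariate".

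Two of the five components have cut-offs that depend on sex: "Waist circumference, cm > 88 (women), > 102 (men") and "HDL cholesterol, mg/dL < 50 (women), < 40 (men"). The triglyceride, glucose and blood pressure criteria are common to both sexes.

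Sex does not enter through the strata. SAP 1.2 says: "Randomization will be stratified by diagnosis (schizophrenia/schizophreniform disorder vs bipolar I disorder), region (US vs non-US), and baseline BMI". SAP 3.8.5 uses sex only as a subgroup factor for the primary and secondary endpoints.

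On status, SAP 3.8.6 says that for other endpoints "presentation of analysis results will be limited to estimated treatment effect, 95% CI and/or descriptive statistics". The metabolic syndrome text ends: "Data are based on observed values with no imputation for missing values".

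**The concern.** For an outcome defined by crossing a threshold, the useful baseline information is how far the subject starts from that threshold. SAP 3.8.6 follows this elsewhere: BMI categories are adjusted for baseline BMI, and blood pressure categories for baseline systolic and diastolic pressure. That works because those cut-offs are the same for everyone. For waist and HDL they are not, so the same baseline measurement stands for two different risks.

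At stake is how much the two models can show from data already collected. Waist follows from the weight effect under study, and HDL is one of the metabolic outcomes that motivate the product. The syndrome model is not affected, because baseline syndrome status already carries the sex-specific cut-offs.

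**Working it through.** **The plan's own figure.** The documents give no power or precision figure for these models. The only related figure is the primary sample size (SAP 2): difference 8.5 − 5 = 3.5 points, SD 8, 35% dropout, 200 per arm, at least 90% power. Completers per arm are 200 × 0.65 = 130. Power = Φ(3.5 / (8 × √(2/130)) − 1.96) = Φ(3.527 − 1.96) = 94.1%. The stated bound holds and this point does not touch it. I take 130 per arm as the number observed at Week 12.

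**What the covariate measures.**
- Waist 92 cm: a woman is 92 − 88 = 4 cm above her cut-off; a man is 102 − 92 = 10 cm below his.
- HDL 45 mg/dL: a woman is 5 below 50 and meets the criterion; a man is 5 above 40 and does not.
- With the same arm and strata, the model must give both the same risk. The BMI stratum cannot separate them, because its cut-off of 25 is common to both sexes.

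With x the baseline measurement, the distance to the cut-off is x − 102 + 14 × female for waist and x − 40 − 10 × female for HDL. Using distance fixes the sex shift at the cut-off gap and adds no parameter. Adding sex as a factor estimates that shift freely and adds one.

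**Simulation (1,500 trials per scenario).** All inputs are assumptions:
- BMI mean 23.5, SD 3, below 30; women 20%, 35% or 50%
- baseline waist 84 cm (men) and 78 cm (women), plus 2.2 cm per BMI unit, residual SD 5; change +4 cm on olanzapine and +2 cm on ALKS 3831, SD 5
- baseline HDL 47 and 55 mg/dL, SD 11; change −4 and −2 mg/dL, SD 7

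Every model has treatment and all three strata. The baseline term is: A, the measurement (SAP, natural reading); B, A plus sex; C, measurement minus sex-specific cut-off; D, criterion met or not met. Variance is that of the standardized risk difference, relative to A.

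| Outcome, n per arm, % women | Power A / B / C / D (%) | Variance B / C / D |
|---|---|---|
| Waist, 200, 35 | 25.1 / 37.7 / 37.9 / 29.1 | 0.613 / 0.610 / 0.856 |
| Waist, 130, 35 | 18.2 / 27.0 / 27.1 / 18.9 | 0.678 / 0.672 / 0.848 |
| Waist, 130, 50 | 19.9 / 28.0 / 28.2 / 21.7 | 0.602 / 0.595 / 0.823 |
| Waist, 130, 20 | 16.1 / 23.7 / 23.3 / 15.9 | 0.711 / 0.700 / 0.905 |
| HDL, 200, 35 | 34.9 / 38.9 / 39.0 / 31.3 | 0.832 / 0.827 / 1.046 |
| HDL, 130, 35 | 25.7 / 30.0 / 30.0 / 24.9 | 0.841 / 0.831 / 1.030 |
| HDL, 130, 50 | 24.8 / 30.6 / 30.6 / 24.7 | 0.862 / 0.859 / 1.072 |
| HDL, 130, 20 | 26.1 / 28.3 / 28.1 / 21.3 | 0.891 / 0.891 / 1.130 |

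B and C perform alike.

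**Odds-ratio scale (130 per arm, 35% women, A to B).**
- Waist: median log odds ratio −0.476 (SE 0.447) to −0.804 (SE 0.603). The ratio of estimate to SE goes from 0.476/0.447 = 1.06 to 0.804/0.603 = 1.33.
- HDL: −0.456 (SE 0.342) to −0.557 (SE 0.380); ratio 1.33 to 1.47.

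The SE rises, but the estimate moves further, so power rises. The mean risk difference barely moves (waist −0.0385 to −0.0397), while its SD falls from 0.0368 to 0.0303; (0.0303/0.0368)² = 0.678.

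**No treatment effect (130 per arm, 35% women).** Rejection rates are 4.9% (A) and 5.9% (B) for waist, and 6.0% and 6.4% for HDL. Simulation error is √(0.05 × 0.95/1500) = 0.56 points.

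**Other assumed inputs.**
- 260 observed, waist 86 and 79 cm, SD 8.5–10, 50–60% men, BMI stratum only, A against B: for a 2 cm effect, power 22.3% to 31.9%; for 3 cm, from 37.9–42.2% to 53.7–59.0%. HDL at 48 and 56 mg/dL, SD 11: 42.9% to 49.4% (3 mg/dL) and 66.3% to 73.9% (4 mg/dL).
- A further set with all strata: waist 21% to 28% and 44% to 57%, HDL 48% to 52%; variance about 27–37% lower for waist and 19% lower for HDL.
- Leaner baselines (84 and 74 cm, SD 8.5; or 84 and 75 cm, SD 7) with a 2 cm effect: about 24 and 19 waist events in 260, and a gain of about 5–7 points.

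**The case against.** The case for leaving the text alone is substantial.

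- A reader might infer that the planned odds ratio is biased, because it lies nearer 1. The documents do not support that. Treatment is randomized, so omitting sex confounds nothing, and type I error holds. Much of the shift is non-collapsibility: an odds ratio conditional on a strong predictor is a different and larger quantity.
- A reader might expect the fix to tighten the reported interval. If the reported effect is the odds ratio, the natural output of a logistic model, the interval widens on the log scale. The precision gain belongs to the risk difference, which the SAP does not request for these endpoints.
- No decision hangs on the power gain. The endpoints carry no alpha, and the arm effect is analysed elsewhere without sex-specific cut-offs: waist change (secondary, ANCOVA with MI), waist increase of at least 5 cm (logistic with MI), and HDL change (MMRM).
- Baseline value could mean met or not met, since the parent model uses baseline syndrome status. That reading already carries the sex-specific cut-off.
- Entry BMI below 30 may leave few waist events, and every simulated size is assumed.

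All of this stands and limits the importance of the point. It does not remove it. The measurement is the more natural reading, because the SAP changes its wording from syndrome status to baseline value. Status discards distance: in the table it lowers variance by 10–18% for waist but raises it by 3–13% for HDL. Under either reading the SAP should say which is meant.

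**Conclusion.** The point holds as a minor improvement. Read as the measurement, the waist and HDL covariate does not order subjects by distance to their own threshold, and efficiency is lost. Across the assumed inputs, the planned model gives up about 5–20 points of power for waist and 2–8 for HDL. The corrected covariate cuts the variance of a standardized risk difference by about 27–40% and 11–19%. These sizes rest on assumed means, SDs, effects and sex mix; the direction was the same in every scenario with a treatment effect.

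The planned analysis is valid, and no claim of the trial changes.

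**What to change.** In SAP 3.8.6, for the waist and HDL component models only:

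1. Use the measured baseline value minus the subject's sex-specific cut-off as the covariate, or keep the measurement and add sex as a factor. The distance form is preferable because it adds no parameter and performed the same.
2. State that baseline value means the measurement, not criterion status.
3. Report the standardized risk difference with its 95% CI beside the odds ratio. SAP 3.8.3.1.1 already reports a risk difference with a CI for the weight-gain proportions.

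Leave the other component models unchanged. The cost is one clause before unblinding, using data already collected. Under SAP 5, a change to a non-confirmatory analysis needs to be listed and explained in the study report. The downsides are a wider interval on the log odds-ratio scale and, if sex is added as a factor, one more parameter in a model that may have few waist events.
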